7.1.4 Adverse Event of Special Interest

New onset or worsening arthralgia that is medically attended will be included as an AESI. The occurrence of new onset or worsening arthralgia that is medically attended will be monitored throughout the study for all subjects. Medically attended visits include hospital, emergency room, urgent care clinic, or other visits to or from medical personnel.

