8.3.2 Secondary Endpoints

- Incidence of solicited AEs through Day 8.
- Incidence of unsolicited AEs through Day 29.

- Incidence of AESIs and SAEs through end of the study.

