1 INTRODUCTION

This Statistical Analysis Plan (SAP) is based on Protocol EBSI-CV-317-010, “A Phase 2 Open-Label Study to Assess the Safety and Immunogenicity of PXVX0317 (Chikungunya Virus-Like Particle Vaccine [CHIKV VLP], alum-adjuvanted) (Version 4.0 07-DEC-2021). This document specifies details of the definitions of the derived variables, analysis methods, assumptions, and data handling conventions. The document is accompanied by mock-up tables, listings, and figures (TLF shells). Some further details on the calculation of derived variables will be provided as programmer’s notes in the TLF shells. The TLF shells serve only as a guide for programming the final TLF. They are working documents and can be updated as needed.

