6.3 Derived Variables

This section provides definitions of the derived variables. In some cases, the definitions are provided in the relevant sections as noted.

AE, causing study discontinuation, is defined as a Yes response to the corresponding question on the AE eCRF.

AE, medically attended (MAAE), is defined as a Yes response to the corresponding question on the AE eCRF.

AE, related, is defined as one that is “probably” or “possibly” related to IP per Investigator assessment on the eCRF. If the relationship is missing for one or more occurrences of an AE for a given subject, the closest relationship of the remaining occurrences of the AE for that subject will be used; if the relationship is missing for the only occurrence of an AE for a given subject, then that event will be assumed to be related in order to be conservative.

AE, resulting in death, is defined as a Yes response to the corresponding question on the AE eCRF and/or a fatal outcome.

AE, serious, is defined per the derived eCRF field for AE seriousness, based on the individual criteria that make an AE qualify as serious (results in death, is life threatening, requires inpatient hospitalization or prolongation of existing hospitalization, results in persistent or significant disability/incapacity or is a congenital anomaly or birth defect, or any important medical event such as an event that may jeopardize the subject or require medical or surgical intervention to prevent one of the above outcomes).

AESI is defined in this study as new onset or worsening arthralgia that is medically attended, as noted by an AE coded to any of the narrow or broad preferred terms included in the MedDRA Standard Query (SMQ) for arthritis (see Appendix III) or having a Yes response to the corresponding AESI question on the AE eCRF.

AE, severity, is graded Grade 1 (mild) to Grade 4 (potentially life-threatening) as described in Section 5.8. If the severity is missing for one or more occurrences of an AE for a given subject, the maximum severity of the remaining occurrences of the AE for that subject will be used; if the severity is missing for the only occurrence of an AE for a given subject, then that event will be assumed to be severe in order to be conservative.

AEs, solicited, are defined as those collected in the memory aid. Solicited AEs include local (i.e., pain, redness, and swelling) and systemic reactions (i.e., fever, chills, fatigue, headache, myalgia, arthralgia, and nausea).

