9.2.1 Overall Summary of Solicited and Unsolicited Adverse Events

A high-level summary of solicited and unsolicited AEs combined will review the frequency counts and percentages of subjects reporting AEs in each of the following categories:

- Any AE and any AE \geq Grade 3
- Any solicited AE and any solicited AE \geq Grade 3
- Any treatment-related solicited AE and any treatment-related solicited AE \geq Grade 3
- Any unsolicited AE and any unsolicited AE \geq Grade 3
- Any treatment-related unsolicited AE and any treatment-related unsolicited AE \geq Grade 3
- Any SAE
- Any treatment-related SAE
- Any AE leading to study discontinuation
- Any fatal AE
- Any AESI (see definition in Section 6.3)
- Any MAAE and any treatment-related MAAE

In addition, summaries of combined solicited and unsolicited AEs by SOC, PT and highest reported severity will be provided for the following populations:

- Safety population by sex

- Safety population by race group

9.2.2 Solicited Adverse Events from Day 1 until Day 8

Solicited AEs recorded daily in the memory aid until Day 8 include local (i.e., pain, redness, and swelling) and systemic reactions (i.e., fever, chills, fatigue, headache, myalgia, arthralgia, and nausea). In addition, solicited AEs ongoing after seven days post-injection (Day 8) will be also recorded as unsolicited AEs. Severity of solicited AEs will be assessed by the Investigator in the same manner as unsolicited AEs.

Frequencies and percentages of subjects experiencing each solicited AE will be presented by maximum severity. The following summaries of solicited AEs will be produced:

- Solicited AEs by maximum event severity, for each event and for any event
- Solicited AEs of severe (Grade 3) or higher severity, for each event and for any event
- Treatment-related solicited AEs by maximum event severity, for each event and for any event
- Day of first onset of solicited AEs, for each event and any event
- Duration of solicited AEs, for each event and any event
- Solicited AEs by day post-injection for each event and for any event

Occurrence of at least one AE by category (local, systemic) for solicited AEs will also be included. Only subjects with at least one observation (i.e., any non-missing values but excluding “Not done/unknown”) for the solicited AEs will be summarized.

9.2.3 Unsolicited Adverse Events from Day 1 through Day 29

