9.3 Deaths, Other Serious Adverse Events and Other Significant Adverse Events

9.3.1 Deaths from Day 1 to Day 183 End of Study Visit

Deaths are not expected in this study with healthy participants. A tabulation and subject data listing of AEs leading to death will be provided.

9.3.2 Serious Adverse Events from Day 1 to Day 183 End of Study Visit

SAEs will be tabulated according to MedDRA SOC, PT and highest reported severity. A separate tabulation will be limited to treatment-related SAEs only. A subject data listing of all SAEs will be provided.

9.3.3 Adverse Event of Special Interest from Day 1 to Day 183 End of Study Visit

AESI (see definition in Section 6.3) will be tabulated according to MedDRA SOC, PT and highest reported severity.

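### SAP 6.3 does not tie the Arthritis SMQ route to medical attendance, so an AESI count programmed from its named fields could go beyond protocol 7.1.4

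*SAP*

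**What the plan says.** Protocol 7.1.4 names one AESI: "New onset or worsening arthralgia that is medically attended will be included as an AESI". Its incidence belongs to a secondary endpoint in protocol 8.3.2: "Incidence of AESIs and SAEs through end of the study".

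SAP 6.3 starts from the same definition and then gives two ways to recognise the event. The first is "new onset or worsening arthralgia that is medically attended, as noted by an AE coded to any of the narrow or broad preferred terms" of the Arthritis SMQ, listed in SAP Appendix III. The second is joined to it by an OR: "or having a Yes response to the corresponding AESI question on the AE eCRF".

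The same section defines attendance as a variable of its own: "AE, medically attended (MAAE), is defined as a Yes response to the corresponding question on the AE eCRF". The AESI entry does not refer to that variable.

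The output sections add no condition. SAP 9.2.1 has a row for "Any AESI (see definition in Section 6.3"), and SAP 9.3.3 says "AESI (see definition in Section 6.3) will be tabulated according to MedDRA SOC, PT and highest reported severity". SAP section 1 leaves some derivation detail to the table shells: "Some further details on the calculation of derived variables will be provided as" programmer's notes.

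**The concern.** The protocol event has three elements: arthralgia, new or worse, and medically attended. The SMQ route in SAP 6.3 names a data field for none of them except through the coded term, and the term list is wider than arthralgia. Two programmers working from the same text could reasonably produce different AESI counts, one filtering on MAAE and one not.

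At stake are the AESI table and the AESI row of the overall summary, both of which report a protocol secondary endpoint. If the unfiltered rule were used, events outside the protocol definition would appear under the AESI label. No AESI that the site had flagged would be lost, because the AESI question is enough by itself.

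**Working it through.** The plan states no figure to reproduce here. The check sets the passages side by side and then sizes one misclassification.

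**1. Can an unattended event reach the SMQ route?** Yes. Arthralgia is a solicited event (protocol 3.3.10). If it continues past the solicited period it goes onto the AE form (protocol 3.3.10), is handled as an unsolicited AE (SAP 9.2.3) and is MedDRA-coded (protocol 8.7.2.2). Arthralgia is an Appendix III term. None of these steps requires a medical visit.

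**2. What does the list contain?** Appendix III has 132 distinct terms. By wording, 3 name arthralgia or joint pain: Arthralgia, Infusion site joint pain and Injection site joint pain. That leaves 132 − 3 = 129 others. Many of these are diagnoses that can present as joint pain. A few, such as Neck pain and Spinal pain, are symptoms that are not arthralgia.

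**3. When does the SMQ route change the count?** Only when the AESI question is not Yes, because of the OR. The cases are:

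| Event | AESI question | MAAE | Protocol 7.1.4 | SMQ term alone | SMQ term and MAAE |
|---|---|---|---|---|---|
| New arthralgia, attended | Yes | Yes | AESI | counted | counted |
| Arthralgia past Day 8, no visit | No | No | not AESI | counted | not counted |
| Attended new joint pain recorded as Gout | No | Yes | may be AESI | counted | counted |
| Attended Neck pain | No | Yes | not AESI | counted | counted |

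The MAAE condition corrects the second row. It does not settle the last two, which need a decision on the individual event.

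**4. When could it happen?** Mainly up to Day 29. After that, apart from events around the Day 57 plasmapheresis, only SAEs and AESIs are collected (footnotes 7 and 10 of the Schedule of Events).

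**5. Size.** With all 25 planned subjects in the safety population, one misclassified subject changes AESI incidence by 1/25 = 4.0 percentage points, and two by 2/25 = 8.0. The documents give no arthralgia rate for this product, so the expected number cannot be derived. If attendance is applied to both routes, or the shells already filter, the unattended over-count is zero.

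**The case against.** The strongest reply is that attendance is already in the definition. SAP 6.3 opens with it, and what follows can be taken as the means of finding such events, so the opening governs both routes. That is a fair reading, and a reader who inferred that the SAP had dropped the attendance requirement would be going too far. What stands is narrower: the rule names fields, and MAAE is not one of them.

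A second reply concerns the term list. A reader might infer that Appendix III is wrong and should be cut to arthralgia terms. Protocol 7.1.1 points the other way: it prefers a diagnosis to its symptoms as the recorded term. Attended new joint pain diagnosed as gout would be coded as Gout, so a diagnosis-level search is a reasonable way to find it. Cutting the list could miss such an event whenever the AESI question was not ticked. This reply stands for diagnosis terms. It does not cover Neck pain and Spinal pain.

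Third, a reader might infer that all solicited arthralgia would be swept in. Protocol 8.7.2.2 lists AESI among the unsolicited AE summaries and adds only those solicited events that continue beyond seven days. The SAP's AESI table (14.3.5.6) sits in the unsolicited series. Events resolved by Day 8 therefore appear to be outside the search. The matter is not fully closed, since the AESI row in SAP 9.2.1 is part of a combined solicited and unsolicited summary.

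Finally, there are controls: 24-hour AESI reporting (protocol 7.3.1), recording of confirmed AESIs (7.5.2), tables by preferred term, and the health care encounter listing (16.2.9). They make an unnoticed miscount less likely, but they do not say which events the table should count.

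**Conclusion.** The point holds as a minor gap in a derivation rule. Applied from the fields it names, SAP 6.3 can label as AESI an event that protocol 7.1.4 excludes, and the missing condition is on a field already collected. Confidence is high on the wording gap. The documents do not support a claim that AESI incidence will in fact be inflated: no rate is given, and the shells that may hold the filter are not available here.

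The 4.0 points per subject assumes a safety population of 25 and AESIs reported as counts and percentages of subjects. Any error is toward over-reporting. The study tests no hypothesis (SAP 6.4) and its sample size rests on practical grounds (SAP 4), so neither is affected.

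**What to change.** In SAP 6.3, define AESI as (AESI eCRF question = Yes) OR (Appendix III preferred term AND MAAE = Yes).

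Keep the broad Appendix III list. Send matches that the site has not flagged as AESI back for confirmation that they are arthralgia, new or worse, or show them in a supportive table that is not labelled AESI. This handles terms such as Neck pain without losing joint pain coded as a diagnosis.

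Confirm, in line with protocol 8.7.2.2, that the search covers AE-form events, including solicited AEs that continue past Day 8. If the shells already hold the MAAE filter, move it into SAP 6.3, because the SAP describes the shells as a working guide that can change.

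The cost is one or two sentences, one programming condition, and site queries for any unflagged matches. No new data field is needed.

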8.7.2.2 Unsolicited AEs

All the unsolicited AEs occurring during the proscribed collection period in the study will be recorded, regardless of their assessment of relatedness by the Investigator.

The original verbatim terms used by Investigators to identify AEs in the eCRFs will be mapped to PT using the MedDRA dictionary. The unsolicited AEs will then be grouped by MedDRA PT into frequency tables according to SOC. All reported AEs, as well as AEs judged by the Investigator as at least possibly related to IP, will be summarized according to SOC and PT. When an unsolicited AE occurs more than once for a subject, the maximum severity and strongest relationship to treatment will be counted.

Only treatment-emergent AEs will be summarized (i.e., excluding those after a subject has given informed consent, but before vaccination).

Unsolicited AEs will be summarized by alphabetic SOC and descending PT as follows:

- Any unsolicited AE
- Related (“possibly” or “probably” related) unsolicited AEs
- SAEs
- Related (“possibly” or “probably” related) SAEs
- AESI
- Unsolicited AEs leading to withdrawal
- Any AE leading to death

Listings of all AEs will be provided by subject.

Combined Solicited and Unsolicited AEs: Solicited AEs continuing beyond 7 days after vaccination will be coded by MedDRA and combined with the unsolicited AEs. A summary of subjects with all combined solicited and unsolicited AEs, by SOC and PT, will also be provided.

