5.8 Adverse Event Toxicity/Severity Grading

With the exception of redness and swelling, all solicited AEs are graded by the Investigator according to severity grading scales from "mild" to "potentially life-threatening." The

severity of redness and swelling, recorded as a diameter (mm) in the solicited adverse event memory aid, is summarized according to categories based on the largest-diameter linear measurement when a local reaction is present:

- Grade 0/absent = 0-24 mm.
- Grade 1/mild= 25-50 mm.
- Grade 2/moderate= 51-100 mm.
- Grade 3/severe= >100 mm.
- Grade 4/potentially life threatening = necrosis or exfoliative dermatitis.

Events reported as not present (0 mm is entered) are reported as Grade 0. Similarly, body temperatures recorded by the subject that are below 100.4° result in fever reported as Grade 0/absent.

Unsolicited AEs and solicited AEs other than redness and swelling are graded by the Investigator for severity. The severity grading scales (Grade 1 = Mild, Grade 2 = Moderate, Grade 3 = Severe, Grade 4 = Potentially Life-Threatening) that are used for safety assessment in this study are provided in Appendix II of this document and Section 7.1.7 and Appendix II of the Protocol, based on the *FDA Guidance for Industry: Toxicity Grading Scale for Healthy Adult and Adolescent Volunteers Enrolled in Preventative Vaccine Clinical Trials* (1). Note that AEs that result in death are classified as Grade 4 and indicated as resulting in death.

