All unsolicited AEs occurring during the prescribed collection period in the study will be recorded, regardless of their assessment of relatedness by the Investigator. Unsolicited AEs will include those solicited AEs ongoing after seven days post-injection (Day 8).

All reported unsolicited AEs will be summarized according to MedDRA SOC, PT and highest reported severity. When an unsolicited AE occurs more than once for a subject, the maximum severity and closest relationship to treatment will be counted. The unsolicited AE analysis will include unsolicited AEs judged by the Investigator as at least possibly related to IP.

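### SAP 6.3 assumes the worst for a missing AE severity or relationship only when the event occurs once, so a further known occurrence can lower the subject's result

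*SAP*

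**What the plan says.** SAP 6.3 (Derived Variables) gives two pairs of rules.

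- **Severity.** If the AE occurred once in the subject and has no grade, "then that event will be assumed to be severe in order to be conservative". If there are other occurrences, the entry reads "If the severity is missing for one or more occurrences of an AE for a given subject, the maximum severity of the remaining occurrences" and takes that value for the AE.
- **Relationship.** If the AE occurred once and has no relationship, "then that event will be assumed to be related in order to be conservative". If there are other occurrences, "the closest relationship of the remaining occurrences of the AE for that subject will be used".

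SAP 5.8 fixes the labels: "Grade 1 = Mild, Grade 2 = Moderate, Grade 3 = Severe, Grade 4 = Potentially Life-Threatening". An event assumed severe is therefore Grade 3. SAP 6.5 adds no rule for missing severity or relationship and refers back to 6.3.

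Two other places say how repeated unsolicited AEs are counted within a subject. In SAP 9.2.3 "the maximum severity and closest relationship to treatment will be counted". In Protocol 8.7.2.2 "the maximum severity and strongest relationship to treatment will be counted". Neither says what to do with a missing value.

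**The concern.** The same missing field gets opposite treatment depending on whether the subject had the AE again. Alone, the unknown occurrence counts as the worst plausible case. With a known occurrence beside it, it counts for nothing. The subject-level result can then improve because a further event was recorded.

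The outputs that depend on these rules are:

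- the Grade 3-or-higher and treatment-related rows of the high-level summary (Table 14.3.2.1);
- the severe and treatment-related solicited AE tables (14.3.2.3 and 14.3.2.4);
- the severity columns of the AE tables;
- entry to the treatment-related tables, such as 14.3.5.3 and 14.3.5.5.

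Safety is the only secondary objective and about 25 subjects are planned, so a single subject can decide whether a row reads none or one.

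**Working it through.** The plan states no figure on this point, so there is none to reproduce. The check applies the wording of SAP 6.3 literally to the occurrences of one AE in one subject.

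**Rules as written**
- Severity = maximum of the known grades if any is known; Grade 3 if there is one occurrence and its grade is missing.
- Relationship = closest of the known relationships if any is known; related if there is one occurrence and its relationship is missing. Possibly and probably related both count as related (SAP 6.3).

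**Comparison rule:** set each missing severity to Grade 3 and each missing relationship to related, then take the maximum severity and closest relationship.

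In the table, U is an occurrence with both fields missing.

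| Occurrences of the AE | SAP 6.3 | Each missing value set first |
|---|---|---|
| U alone | Grade 3, related | Grade 3, related |
| U + Grade 1, unrelated | Grade 1, unrelated | Grade 3, related |
| U + Grade 2, unrelated | Grade 2, unrelated | Grade 3, related |
| U + Grade 3, unrelated | Grade 3, unrelated | Grade 3, related |
| U + Grade 1, possibly related | Grade 1, related | Grade 3, related |
| U + Grade 4, possibly related | Grade 4, related | Grade 4, related |
| U + U | no rule applies | Grade 3, related |

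**What the table shows**
1. From row 1 to row 2 the unknown occurrence is the same, yet the result falls from Grade 3, related to Grade 1, unrelated.
2. The fields move separately. In row 4 only the relationship falls; in row 5 only the severity falls. A fall in both needs both fields missing and a companion that is below Grade 3 and unrelated.
3. A known occurrence of Grade 3 or above removes the severity difference, and a known related one removes the relationship difference (row 6 does both).
4. A true maximum cannot fall when an occurrence is added. The maximum in SAP 9.2.3 and Protocol 8.7.2.2, combined with 6.3, can.
5. Row 7 is an adjacent gap: no known occurrence remains, and neither is the only one.

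**Size.** With the SAP 2.2 target of 25 subjects as denominator, one subject is 1/25 = 4.0%. For scale, the Wilson 95% interval is 0.7% to 19.5% for 1/25 and 0.0% to 13.3% for 0/25; the SAP does not plan these intervals for AE rows. The 4.0 points is a maximum. The summary rows count subjects with any qualifying AE, so a subject already there through another AE does not move the row. A subject missing one field can move only the rows for that field.

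**The case against.** The rule can be read as a sensible hierarchy: use the subject's own worst observed value for that AE, and assume the worst only when nothing is observed. It still takes a maximum over the known values. A reader might infer that the repeated-event rule defeats its own stated purpose. The text does not support that, because the conservative rationale is attached only to the single-occurrence clause in each sentence. What stands is that the two clauses treat the same unknown differently.

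A reader might also infer that reporting more events generally improves the safety result. It does not. The further occurrence must be of the same AE in the same subject, with a known grade below 3 or a known unrelated assessment.

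The trigger may be rare. The investigator grades every AE and assesses causality (Protocol 7.1.7, 7.1.8). Edit checks, manual review, queries, investigator sign-off and sponsor review before lock follow (Protocol 9.3). Redness and swelling grades come from diameters (SAP 5.8), and AEs are listed by subject. All of this limits how often the rule is needed. It does not make the rule coherent, and it would equally make the single-occurrence rule unnecessary.

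Worst-case imputation also has a price: it can override a known mild grade with an assumed Grade 3, and one false Grade 3 can move a row by up to the same 4 points. SAP 6.5.4 deliberately sets implausible memory-aid grades to missing and excludes them, so a blanket imputation could count an excluded value as severe. Both points stand, and the second calls for an exception in the fix.

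**Conclusion.** The inconsistency is real and follows from the wording of SAP 6.3. Nothing in SAP 6.5, SAP 9.2.3 or Protocol 8.7.2.2 repairs it. Its practical effect is small and may be nil: the documents give no expected rate of missing severity or relationship, and if queries resolve every value, no count changes.

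Where a value does stay missing, one subject moves a Grade 3-or-higher or treatment-related row by at most 4 percentage points, provided no other AE already places the subject in that row. This assumes a denominator of 25. Enrolment is approximate, subjects may be replaced, and solicited summaries include only subjects with at least one observation, so the actual denominator may differ.

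A reader might infer that the numbers of SAEs or AESIs are affected. They are not: entry to those tables rests on seriousness fields, coding or a separate eCRF answer. Only their severity columns and the treatment-related subsets can change. The point is minor, but worth correcting before the final analysis.

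**What to change.** Reword the severity and relationship entries in SAP 6.3 so that each occurrence with missing severity is set to Grade 3, and each with missing relationship to related, before the subject-level maximum severity or closest relationship is taken. Except grades set to missing as implausible under SAP 6.5.4; these stay excluded. Footnote the affected tables with the number of values imputed, so that an assumed Grade 3 can be told from an observed one. The same wording covers a repeated AE in which every occurrence is missing.

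The cost is two reworded sentences and the matching programming step. It needs no new data and no new output. The downside is slightly less favourable counts if entries stay missing.
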